### **Enrollment in the follow-up study**

In Phase 1, enrollment in the longitudinal cohort will be offered to eligible patients who have  $CD4 \leq 100$  cells/ $\mu L$  enrolled at and plan to receive ongoing outpatient care at one of the selected study OPCs (Table 2). Those who test plasma CrAg-positive and have no symptoms of meningitis will be treated with high-dose fluconazole. Study participants will be followed from the time of plasma CrAg screening for a minimum of 6 months and up to 12 months depending upon when they are recruited with respect to the study expected duration. Routine clinical data will be abstracted from medical records and supplemental data will be collected to determine treatment outcomes and related factors. Fluconazole will be provided by the study for patients enrolled in the follow-up program during Phase 1 for the duration of the study. For those who tested CrAg-positive and are still receiving maintenance fluconazole at the end of their longitudinal follow up, fluconazole will be provided through routine sources.

In Phase 2, screened patients will not be followed up prospectively. However, fluconazole supply for identified CrAg-positive patients will be provided by the project if patients do not otherwise have access through their OPCs.

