## **Definition of end points**

Retention in care: Patient known to be alive and have visited the clinic in the prior 90 days.

Dead: Patient confirmed or reported to have died.

Lost to follow-up: Follow up will be described in two ways. From the time of enrollment in the study and from ART initiation (routinely collected through retention national indicators). Patients have not returned to the clinics > 90 days from the last clinical appointment for those who initiated ART and > 6 months for those who have not initiated ART without any follow up contacts with their OPCs, have not been reported or confirmed dead, or known to have transferred to other clinics.

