## 6. Sample size calculation:

The two primary outcomes of the study are 1) the estimate of the percentage of prescreened patients who have  $CD4 \leq 100$  cells/ $\mu L$  and 2) Of those with  $CD4 \leq 100$  cells/ $\mu L$ , the estimate of the percentage who are CrAg+. For these primary outcomes, data will come from both Phase 1 and Phase 2. From study initiation to October 31 2016 (approximately 13 months), we prescreened 2,612 participants, and 1068 of these had a  $CD4 \leq 100$  cells/ $\mu L$ . Of those, 957 enrolled, and 25(2.6%) were CrAg+. Assuming a similar enrollment rate (74 per month), upon the completion of Phase 1 (March 2017), we will have prescreened 3,014 participants and would expect 1,232 to have  $CD4 \leq 100$  cells/ $\mu L$  and 1,104 to be enrolled in the follow up study. Of these, we would expect approximately 29 to be CrAg+.

For Phase 2 (presumably from February 2017 to September 2017), plan to prescreen an additional 1,808 patients. Taking both data from Phase 1 and Phase 2 into account, we would expect to prescreen 4,822 patients and to document 1,972 patients with  $CD4 \leq 100$  cells/ $\mu L$ . In total, we would expect approximately 46 patients to be CrAg+.

Table 3 presents confidence limits for the two primary outcomes based on these assumptions and incorporating a design effect (DEFF) to account for the within-facility clustering of observations. The design effect is computed as  $[1+(m-1) \text{ ICC}]$  where  $m$  is the average number of patients per facility and ICC is the intraclass correlation coefficient. There is no local data on which to base assumptions about the magnitude of the within-clinic correlation in Vietnam, but a recent publication reports intraclass correlation coefficients (ICCs) of about .02 or smaller for health-related variables in an HIV-positive clinic population in sub-Saharan Africa [4]. Taking data from Phase 1 into account only, for the first primary outcome,  $m$  is 137 (3014/22) and for the second primary outcome,  $m$  is 56 (1,232/22). Taking data from both Phase 1 and Phase 2 into account,  $m$  is 219 (4822/22) and is 90 (1972/22) for the first and the second primary outcomes respectively.

**Table 3. Precision for primary study outcomes based on projected enrollment in Phase 1 (through March 2017) and Phase 1 + Phase 2 (projected through September 2017)**

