## 7. Study procedures

### 7.1. CrAg Screening Implementation (Reflex testing, return of results, communicating results and enrolment into the prospective cohort)

#### 7.1.1. CrAg screening in study OPCs in Phase 1

As CrAg screening is a WHO and Vietnam MOH national recommendation, it is considered SOC for persons with advanced HIV (CD4≤100 cells/ $\mu$ L), and reflexive testing does not require informed consent. All adult patients presenting for ART evaluation and who provide a sample for CD4 testing will be educated about the risks of OIs such as CM and tested for cryptococcal antigen in accordance with national guidance. They will be specifically informed about CrAg screening prior to their blood draw using a short script (See Appendix 1: Screening , Appendix 2A: Script informing patients of CrAg screening (English)and Appendix).

Patients will be told that those with low CD4 whose CrAg results are positive will be contacted by the clinic to invite them back for an earlier appointment. Results of the CD4 and CrAg tests will be sent to the respective clinics within 24 hours of the tests, and made available to physicians (Appendix 15: CrAg Testing Request Form). Results of the CD4 and CrAg tests will be recorded daily into the evaluation logs at the participating laboratories and respective clinics (see Appendix and Appendix 16: CrAg testing log for the lab).

Once the clinic receives the test results, OPC staff will be responsible for contacting the patients who are CrAg-positive by telephone with the results within 24 hour sand request

them to return to the clinic for an earlier appointment. Three attempts will be made to reach the patient by phone or Short Message Service (SMS) and if not reachable, the patient will be seen at his routine scheduled appointment which is normally within two weeks of the date of CD4 testing. When patients with  $CD4 \leq 100 \text{ cells}/\mu\text{L}$  return to the clinic, they will be informed of the results of both the CD4 and plasma CrAg testing. Procedures for the prospective cohort evaluation and data collection will be described. If the patient agrees to participate, s/he will sign the consent form for enrollment (see Appendix 3A: Inform Consent Form (English)) and will be assigned a study identification (ID) number. This will be considered a study visit since in routine practice, patients only return for their CD4 at the next scheduled visit, usually 1-2 weeks after that date of sample collection.

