## Cryptococcal Retention In Care Study (CRICS)

tested for CrAg. If the patients already had CD4  $\leq 100$  cells/ $\mu$ L within the last 2 weeks, specimens of the remnant plasma from other routine tests or additional blood draws will be used.

- In Vietnam, blood specimens for CD4 counts are kept in storage for quality control purposes as routine practice before being destroyed. For all patients who will undergo CrAg screening (those with CD4  $\leq 100$  cells/ $\mu$ L), remnant plasma after of specimens with will be stored at -20°C until CD4 count result is returned to patients. The samples are only identified by a “serial laboratory number” and not names. We are referring to this as “***temporary routine storage***. Standard logbook of CD4 testing will be kept at the laboratory and individual results will be returned to the OPC as MO mandates.
- When patients return to the clinic—usually within 2-3 weeks—to receive their CD4 results, those with CD4  $\leq 100$  cells/ $\mu$ L will be consented for “enrollment into the study”. Consent will also be sought for “storage of remnant plasma”.
  - a. Patients who consent for study enrollment and for sample storage: Out Patient Clinic (OPC) Staff at participating sites will inform the lab about sample storage for patients who have consented. Their samples will be retrieved from “***temporary routine storage***”; a Study ID will be affixed and the laboratory number erased permanently. All samples will now be stored as “Study Samples in storage”. No other identifying information will be recorded and kept at the laboratory.
  - b. The OPC will inform the lab periodically if patients do not come within the scheduled time usually 2-3 weeks. Their samples will subsequently be destroyed by the lab following the laboratory protocols for disposal of biological specimens. These samples will not bear a study ID.
- The laboratory POC will contact the POC at the OPC by telephone each day with a list of patients and the results of CrAg testing. In addition, the laboratory will return the CrAg and CD4 test results as per their normal CD4 result notification process (e.g., paper laboratory reports delivered weekly).
- Each laboratory will keep a facility list of all patients that were screened for plasma Crag from each participating OPC and the results of the CrAg test. A copy of this list will be retrieved by the OPC during the regular collection of CD4 results.

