#### Overview

Demographic, clinical, treatment, and follow-up data will be obtained through chart abstraction into standardized CRFs. Data from CRFs will then be entered into Epi-Info (CDC, Atlanta).

- At enrollment, eligible patients will have an ‘Enrollment Form’ (see Appendix 4: Enrollment **Error! Reference source not found.**) filled out by OPC clinic staff. Baseline patient variables included in this form are listed in the section “10.1. Patient variables.” Both CrAg-positive and –negative patients are also evaluated for quality of life (see Appendix 17: Health-related Quality of Life Form) on the day of their enrollment.
- ART initiation form (Appendix 5: Starting ART Form):
- A ‘Follow-up Form’ (Appendix 6: Follow-up **Error! Reference source not found.**) will be filled out for both CrAg-positive and –negative patients. All patients will be followed from enrollment for a minimum of 6 months and up to 12 months after ART initiation. The frequency of follow-up will be similar for both CrAg-positive and negative patients except for an additional visits to (i) reduce the dose of fluconazole to 450 mg and begin ART initiation 2 weeks after the baseline visit and (ii) for reduction of fluconazole to 200 mg 8 weeks after the start of that dose (Refer to 7.4. Management of a positive CrAg

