## 13. Ethical considerations

### 13.1 Ethical review and informed consent

The invitation to participate in this Cryptococcal Antigen Screening Program will be sent to all sites (see Appendix 13: Invitation to participate in the Cryptococcal Antigen Screening Program). Ethical approval for this program rollout and evaluation will be obtained from the NHTD Ethical Review board and from the CDC IRB. The protocol, consent forms and other study materials will be submitted. Final permission to conduct the study will be obtained from the MOH.

**Reflex CrAg screening on remnant plasma of all patients with CD4  $\leq 100$  cells/ $\mu$ L:** This testing is considered SOC as screening patients for plasma CrAg is included in the Vietnamese national guidelines and is also recommended by WHO[11].

- **Informed consent for prospective cohort (Phase 1):** Patients who return to the OPC for the CD4 result, will be explained and offered enrollment in the study if they meet

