### **13.2. Waiver of consent (specific items)**

There are a number of routine procedures and quality improvement practices as a part of clinical care from which this study will draw aggregate, de-identified data. Regardless of CrAg screening results, supporting the adherence to therapy through the help of families, peer groups, healthcare workers are recommended by the MOH in accordance with decision No. 3003/QD-BYT [15]. These items for which a waiver of consent is requested include:

- A home visit from a health or a community worker and phone contact if a patient misses his/her appointment is a part of routine practice at study sites. This occurs for patients who have missed an appointment and also for patients lost to follow-up to encourage the patient to return for care and to determine whether the patient has transferred to another clinic, defaulted on treatment, or died. Initially, the patients are to be contacted by phone or, if that fails, a home visit is to be made. We believe that these routine procedures are beneficial to all patients at the sites, not only study participating patients.
- Abstracting CD4 count and CrAg testing results in affiliated labs. The recommendation for CrAg screening was issued by the MOH in decision No. 3047/QD-BYT [16]. We believe that the routine monitoring of baseline CD4 to identify patients with advanced disease and of CrAg results will be beneficial to understand the prevalence of CrAg in select provinces and inform allocation of resources for differentiated care, including management of cryptococcal disease, for patients with advanced disease.

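### Follow-up is counted from CrAg screening, but patients can enter only at a later return visit whose timing depends on the CrAg result, so deaths before entry fall outside 12-month mortality and no count of them is planned

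*Protocol*

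**What the plan says.** Four features of the protocol bear on this point.

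- **Start of follow-up.** Section 3 (Enrollment in the follow-up study) says "Study participants will be followed from the time of plasma CrAg screening for a minimum of 6 months". The Overview in Section 10 says "All patients will be followed from enrollment for a minimum of 6 months and up to 12 months after ART initiation". The end-point definitions in Section 3 describe loss to follow-up in two ways: "From the time of enrollment in the study and from ART initiation". Section 7.7 and Table 4 schedule the 2-, 6- and 12-month visits and the off-study form from ART initiation.
- **Entry to the cohort.** Section 13.1 says "Patients who return to the OPC for the CD4 result, will be explained and offered enrollment in the study". Sections 7.1.1, 7.7 and 9.2 agree: results, explanation, consent and study ID all belong to the return visit. Section 15 starts adverse event capture at signature of the consent form.
- **Timing of the return.** For positive results, Section 7.1.1 says "OPC staff will be responsible for contacting the patients who are CrAg-positive by telephone with the results within 24" hours and has staff ask them to come early. Those not reached after three attempts wait for the routine visit. Patients with a negative result come at the routine visit, put at 1-2 weeks after the draw in Section 7.1.1. Section 9.2 says "The OPC will inform the lab periodically if patients do not come within the scheduled time usually 2-3 weeks".
- **Numbers to 31 October 2016.** Section 6 gives 1,068 prescreened patients with CD4 ≤100 and then states "Of those, 957 enrolled, and 25(2.6%) were CrAg"-positive.

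**The concern.** Someone who dies between the draw and the return visit cannot be enrolled. If the clock starts at the draw, every cohort member is credited with days in which death was impossible. This is immortal time, and it lowers the 12-month proportion. The length of that interval is also tied to the CrAg result, which defines the two groups of primary objective 4.

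Moving the start to enrollment removes the guaranteed survival time but does not bring back the deaths before entry. Starting at ART initiation adds a further death-free stretch. Section 7.6 plans a two-week ART delay for CrAg-positive patients, so that stretch may be longer in the other group.

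Primary objective 4 (12-month mortality by CrAg status) and objective 3 (causes of death) are affected. So is the proportional hazards comparison with a historical CrAg-positive cohort in Section 11, which needs a defined time zero. Section 13.4.1 expects the benefit of early detection to show in early mortality, which is the period being lost.

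**Working it through.** **1. The plan's own figures (Section 6).** 1,068/2,612 = 40.9% and 25/957 = 2.6%; both agree with the text. The protocol gives no mortality rate, event count or precision for objective 4, so there is no stated figure to correct.

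**2. Patients not enrolled.** 1,068 − 957 = 111, and 111/1,068 = 10.4%. The protocol does not divide these into ineligible, refusing, pending, not returned and dead. Pending visits alone could be a sizeable part: 1,068 over about 13 months is 82 per month, or about 19 per week (82 × 12/52), so a return lag of 1 to 3 weeks is about 19 to 57 people.

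**3. Share dying before entry.** With monthly hazard h and a window of t days, share = 1 − exp(−h·t/30.44). The windows for CrAg-negatives (7, 14, 21 days) come from Sections 7.1.1 and 9.2. The hazard (1% to 6% per month), the CrAg-positive return time (2 to 7 days) and the hazard ratio (HR) for CrAg-positives are assumptions. At h = 2% per month:

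| Group | Window | HR 1 | HR 3 | HR 5 |
|---|---|---|---|---|
| CrAg-negative | 7 / 14 / 21 days | 0.46 / 0.92 / 1.37% | – | – |
| CrAg-positive | 2 days | 0.13% | 0.39% | 0.65% |
| CrAg-positive | 4 days | 0.26% | 0.79% | 1.31% |
| CrAg-positive | 7 days | 0.46% | 1.37% | 2.27% |

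Over the full range of 1% to 6% per month and 7 to 21 days, the CrAg-negative share lost is 0.2% to 4.1%.

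**4. Which group loses the larger share?** CrAg-negatives do only if the early HR is below the ratio of the windows. The break-even HR is:

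| CrAg-negative window | CrAg-positive 2 days | 4 days | 7 days |
|---|---|---|---|
| 7 days | 3.5 | 1.75 | 1.0 |
| 14 days | 7.0 | 3.5 | 2.0 |
| 21 days | 10.5 | 5.25 | 3.0 |

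The protocol gives neither the HR nor the CrAg-positive return time, so the order is open.

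**5. Effect on CrAg-negative 12-month mortality, clock at screening and no allowance for late entry.** Assume hazard h for 3 months and h/4 for the next 9. The true risk is 1 − exp(−5.25h). The apparent risk among those who return is 1 − exp(−5.25h + h·t/30.44).

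| h per month | True | 7 days | 14 days | 21 days |
|---|---|---|---|---|
| 2% | 9.97% | 9.55% | 9.14% | 8.72% |
| 4% | 18.94% | 18.19% | 17.44% | 16.67% |

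**6. Comparison with sampling error.** For the projected 29 CrAg-positives, the 95% half-width without clustering is 1.96 × √(0.1 × 0.9/29) = 10.9 points at an assumed 10% mortality, and 1.96 × √(0.2 × 0.8/29) = 14.6 points at 20%. For the projected 1,104 − 29 = 1,075 CrAg-negatives at 10%, it is 1.96 × √(0.1 × 0.9/1,075) = 1.8 points. At h = 2% the understatement in step 5 is 0.42 to 1.25 points.

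**The case against.** The best defence is that objective 4 concerns patients enrolled in care, with the CrAg-positive group defined by fluconazole treatment. A patient who never returned was never treated and lies outside that population. Section 11 plans proportions with confidence intervals rather than a test between the two groups, and delayed entry is the kind of detail an analysis plan may settle. Section 12 already records patient return for results. Section 13.2 already draws on routine tracing, done "to determine whether the patient has transferred to another clinic, defaulted on treatment, or died". Finally, the distortion is small beside the uncertainty in about 29 CrAg-positives.

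Part of this stands. If the target is enrolled patients only, deaths before entry are outside it, but then the clock cannot start at screening as Section 3 says. An analysis plan can handle late entry but cannot supply deaths that nobody recorded, and neither Section 12 nor Section 13.2 commits to counting them by CrAg result. The size argument holds for the CrAg-positive group. It is weaker for the CrAg-negative group, where the illustrated understatement is a sizeable part of the half-width.

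Three stronger readings are tempting but unsupported:

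- *More early deaths are lost among CrAg-negatives, so the comparison is biased against CrAg-positives.* As a count the first part is nearly automatic, since about 97% are CrAg-negative. As a share of each group it depends on the unknowns in step 4. Unreached CrAg-positives wait for the routine visit too, and patients tested on a sample taken on the enrollment day (Section 7.7, Visit 0) may have a shorter gap.
- *Patients admitted to hospital before returning are never enrolled.* No passage bars them or sets a last enrollment date, and Section 13.1 lets a representative be approached when a patient cannot consent.
- *Many of the 111 died.* Nothing in the document gives any share. Disposal of non-returners' plasma under Section 9.2 concerns specimens, not outcomes.

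**Conclusion.** The point holds in a limited form and is worth correcting. Section 3 sets an origin that precedes any possible entry, other sections use different origins, and the gap before entry normally depends on the CrAg result. Twelve-month mortality counted from screening is therefore too low as an estimate for screened patients. The loss of early deaths is likely to be unequal between the groups, with direction and size unknown.

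Under the assumed 2% to 4% early monthly mortality and a 7- to 21-day window, the understatement in CrAg-negatives is about 0.4 to 2.3 percentage points. These figures rest on assumed hazards and on every patient returning at the end of the window, so they show scale only. The one figure from the document, 111 of 1,068 (10.4%) not enrolled, is an upper bound on loss before entry because it mixes several reasons.

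**What to change.** 1. **State one time origin** in Section 3 and use it in Section 11 for objective 4 and the proportional hazards analysis. If it is the CrAg specimen date, let each participant contribute time only from the consent date (delayed entry) and estimate 12-month mortality by survival methods on that basis. With so few CrAg-positives, few may be at risk in the first days, so the estimate should be reported as conditional on survival to the first day with an adequate number under observation. If the origin is enrollment, say that the result describes patients who survived to return.
2. **Report attrition before entry.** From the laboratory's list of screened patients (Section 9.2), the clinic screening log (Appendix 14A) and routine tracing (Section 13.2), give de-identified counts by CrAg result of patients with CD4 ≤100 who died or did not return before enrollment. Leave out those who refused consent, since Section 13.1 allows no data from them. Show 12-month mortality again with the known pre-entry deaths added, as a sensitivity result.

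The cost is protocol wording, a change of analysis method and a small tabulation from records that already exist. Some non-returners' outcomes will stay unknown, and the IRB should confirm that the waiver covers the tabulation.

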## **Definition of end points**

Retention in care: Patient known to be alive and have visited the clinic in the prior 90 days.

Dead: Patient confirmed or reported to have died.

Lost to follow-up: Follow up will be described in two ways. From the time of enrollment in the study and from ART initiation (routinely collected through retention national indicators). Patients have not returned to the clinics > 90 days from the last clinical appointment for those who initiated ART and > 6 months for those who have not initiated ART without any follow up contacts with their OPCs, have not been reported or confirmed dead, or known to have transferred to other clinics.

## **4. Study population**

### **Eligibility criteria for Phase 1.**

#### **4.1. Inclusion criteria:**

- Aged  $\geq$  18 years (having passed 18th birthday using Western calendar)
- Confirmed HIV infection using National Testing Algorithm
- CD4  $\leq$  100 cells/ $\mu$ L
- Able to provide written informed consent
- Enrolled at and plan to receive ongoing outpatient care at one of the selected study OPCs

